8.4 Risk Mitigation

All reported ADEs and DDs will be reviewed regularly by the Sponsor for the duration of the clinical investigation to facilitate early detection and appropriate intervention if events are unanticipated with respect to incidence, severity, or outcome.

Respective clinic will handle the Covid-19 situation according to local regulations and instructions.

8.5 Risk-to-Benefit Rationale

The long-term risks using this Osia 2 System is still unknown. In relation to the individual benefit to be more closely monitored regarding the IMD and also get the opportunity to meet and interact more with the audiology team and other medical staff at the clinics the benefits are considered to outweigh the risks. Participation in this clinical investigation could lead to increased risk for the subject to be infected by COVID-19 when visiting the clinic but is judged as limited as long as the subjects and clinics follow local regulations.

9 STATISTICAL CONSIDERATIONS

9.1 General Considerations

The distribution of continuous variables as well as change in continuous variables will be given as n, mean, SD, SEM, Median, Min and Max and the distribution of dichotomous and categorical variables will be given as number and percentages. Mean changes over time will be presented along with 95% CI.

All data will be presented in summarized tables and figures along with listings of individual data. The last non-missing measurement from the CBAS5751 investigation (3- and 6-months visits) will serve as the baseline reference in this follow up analysis for each subject. Changes from this baseline measurement will be evaluated statistically using a paired statistical methodology, each subject serves as his/her own control. Data collected at 12 and 24 months will be presented by visit where applicable. Data which are of collected continuously over time such as Adverse event and Device deficiency will be presented as Number of events and Number of subjects with events, and not by visits. Efficacy audiology measurements will be compared to the subjectively evaluation of the satisfaction with the system in order to find out if there are any useful clinical audiological cut-offs where a subject is satisfied or not.

Analyses at 12 months will be based on subjects attending the 12 months visit and analyses at 24 months analyses will be based on subjects attending the 24 months visit. No per protocol analyses will be performed and no imputation of missing data will be made.

Pass/fail criteria to be applied to the results:

- The objective is considered as fail if more than two of the subjects have experienced a related serious adverse event with the same root cause within the first 24 months from surgery.
- The objective is considered as fail if more than two of the subjects have an increase in PTA-4 Sound field threshold >15 dB at 24 months compared to the last obtained aided PTA value in CBAS5751 (3 or 6 months).
- The objective is considered as fail if more than two of the subjects have an increase in SNR field threshold >1 unit at 24 months compared to the last obtained aided SNR value in CBAS5751 (3 or 6 months).

If a failed result regarding PTA-4 or SNR is obtained a root cause analysis will be performed to confirm that the failed value depends on declined performance and not on other factors such as impaired unaided hearing, incorrectly performed tests or other causes.

If any of the criteria are failed the investigation is considered as fail.

No formal hypothesis testing will be performed in this long term follow up study.

No termination of the study will be made on statistical grounds.

Protocol deviations will be listed in listing appendix.

No Statistical Analysis Plan (SAP) is planned to be produced.

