7 DESIGN OF THE CLINICAL INVESTIGATION

7.1 General

This is a multicentre, open, long term clinical investigation evaluating safety, performance and Patient Reported Outcomes (PRO) with the Osia 2 System in adult subjects 18 years or older with conductive hearing loss, mixed hearing loss or single-sided sensorineural deafness.

The subjects are the participants who performed the 3- and/or 6-month visit in the completed CBAS5751 investigation. The maximum number of subjects will be 27 from three clinics. The subjects will be followed at two visits, 12 and 24 months after the surgery date in the CBAS5751 investigation. The visit window at the 12-month visit will be opened as much as ± 5 months. The reason for this is to enable for as many subjects as possible to be included. At the time of investigation start the seven first implanted subjects in the CBAS5751 investigation have already passed their 12-month timepoint by several months. The performance of the device is not expected to change over this time period, but if it does, it will still be captured. This approach also provides the opportunity to collect safety data from the first seven subjects. At the final and most important time point 24 months, the visit window will be narrowed to ± 4 weeks.

The subjects will attend two scheduled investigation visits over a 12-month investigation period to be assessed as described in the Schedule of Events (Section 3). At investigation visits, subjects will be evaluated through objective audiological hearing tests, patient reported outcomes, questionnaires and safety assessments. The overall outcomes are to determine the hearing performance of the Investigational device at 12 and 24 months post-surgery and compare it with the last performed measurement (3 or 6 months) in the clinical investigation CBAS5751, assessed by sound-field thresholds audiometry, [PTA4, Mean of 0.5, 1, 2 and 4 kHz] and individual frequencies [0.25, 0.5, 0.75, 1.0, 1.5, 2.0, 3.0, 4.0, 6.0 and 8.0 kHz] and Adaptive speech recognition in noise. The self-reported outcomes will also be followed-up and compared with previous reported values. Safety will be assessed by recording and summarising all AEs/ADEs and DDs. A compilation of all AEs and DDs will be performed after all subjects have completed their 12-months visit. A full clinical investigation report will be prepared after the 24-month statistical analysis has been performed.

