7.2.2 Exclusion Criteria

Subjects who meet any of the exclusion criteria described below will not be eligible for this clinical investigation.

1. Unable to follow investigational procedures, e.g. to complete quality of life scales, or unwilling to comply with the requirements of the clinical investigation as determined by the investigator
2. Use of ototoxic drugs that could be harmful to the hearing, as judged by the investigator

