7.2.5 Recruitment & Investigation Duration

The following subject status definitions apply:

- Consented: Signed consent and eligibility evaluations underway
- Screen Fail: Subject determined not to be eligible to proceed for participation
- Enrolled: First use of the Investigational device following completion of screening activities and confirmation of eligibility
- Withdrawn: Enrolled subjects who withdraw or are withdrawn by the Investigator or Sponsor before the expected last visit.
- Complete: Enrolled subjects who complete the planned follow up visits according to this CIP.

The enrolment period for the clinical investigation is anticipated to be four months from the time of first subject consent to enrolment of the last subject.

The expected duration of each subject's participation in the clinical investigation, is 12 months, from the time of informed consent through to the End of Investigation visit 12 months after visit 1.

Clinical Investigation completion is last subject last visit. The anticipated total duration of the clinical investigation is 17 months, including visit windows and follow-up time in the event of an ongoing SAEs/SADEs at the time of this last visit. Ongoing SAEs/SADEs will extend the clinical investigation completion for a further 30 days, or until resolution or stabilisation of the event, whichever comes first.

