8.3 Risks Associated with Participation in the Clinical Investigation

The subjects are already implanted with the investigational device and using the Sound Processor, no additional risk is therefor expected for participation. The long-term risk of using the Osia System is unknown, which will be followed in this investigation in a controlled way until 24 months post implantation.

Due to the current COVID-19 pandemic it could be a potential risk for the subjects to visit the clinics in case of increased outbreaks in the respective regions.

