9.5 Analysis Populations

Subjects attending the 3- and/or the 6-months visit in the original CBAS5751 study who accept to participate in this long term follow up *investigation* and attends the 12- or 24 months visit will be analysed. No per protocol population will be defined.

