17 SUSPENSION OR PREMATURE TERMINATION

The Sponsor will discontinue the clinical investigation site if:

- 1) major non-adherence to the CIP or GCP principles is occurring
- 2) it is anticipated that the subject recruitment will not be adequate to meet the objectives of the clinical investigation

An ongoing clinical investigation may be discontinued in case of:

- 1) device failure
- 2) serious or intolerable ADE, leading to the explant or discontinued use of the device
- 3) subject's death

Should the Sponsor discontinue the clinical investigation, the Sponsor will continue to support those subjects who were already implanted with the device under investigation until the IMD is approved by national regulatory authority.

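### Criterion 1 counts related SAEs from surgery, but its population is set by joining at month 7 to 17, so an SAE in an implanted subject who does not join can be missed

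*Combined protocol and SAP*

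**What the plan says.** Criterion 1 (section 9.1) is failed if more than two subjects have "a related serious adverse event with the same root cause within the first 24 months from surgery". One failed criterion fails the whole investigation.

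The population is formed later. Consent and eligibility take place at Screening/Visit 1, for which section 7.1 states: "The visit window at the 12-month visit will be opened as much as ± 5 months". Section 9.5 limits the analysis to subjects from CBAS5751 who agree to take part "and attends the 12- or 24 months visit will be analysed". Section 7.2.3 caps the number at 27; section 4.2.2.1 reports 29 implanted.

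On subjects who no longer use the device, the sections differ:

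- Section 7.2.1 asks only for a 3- and/or 6-month hearing assessment in CBAS5751 and for consent. Current use is not required.
- Section 7.2.2 excludes a subject who is "Unable to follow investigational procedures", as judged by the investigator.
- Section 7.2.5 defines status as "Enrolled: First use of the Investigational device following completion of screening activities and confirmation of eligibility".
- Section 7.2.5 also has "Withdrawn: Enrolled subjects who withdraw or are withdrawn by the Investigator or Sponsor before the expected last visit", so the safety follow-up offered on withdrawal in section 7.2.6 reaches enrolled subjects only.
- Section 8.3 takes for granted: "The subjects are already implanted with the investigational device and using the Sound Processor".

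**The concern.** The period at risk and the population at risk do not match. The criterion claims the full 24 months from surgery, but a subject enters the count only by joining months later. If a serious complication is the reason for not joining, the event removes a subject from the count when it should add one. The rule is an absolute count, not a proportion, so a missed subject can only lower it.

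The exposed interval runs from the last CBAS5751 visit to Visit 1. A subject explanted in that time is outside the parent study's follow-up and may not be admitted to this one. Two sites could treat the same subject differently: one could enrol under 7.2.1, the other could screen-fail under 7.2.2 or 7.2.5. Section 9.1 says that no separate SAP is planned, so no later document is due to settle the matter.

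The study is meant to supply long-term safety data to regulators (section 4.3). A pass would be read as a statement about all implanted subjects from surgery on, although it covers only those who joined.

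**Working it through.** **1. When the population forms.** Section 7.1: 12 ± 5 months gives month 7 to 17. The schedule in section 3 gives ± 22 weeks: 22 × 7 / 30.4375 = 5.06 months, so month 6.9 to 17.1. The two agree.

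**2. The exposed interval.** For a subject last seen at month 6 in CBAS5751, it is 6.9 − 6 = 0.9 to 17.1 − 6 = 11.1 months. Section 7.1 says the first seven implanted subjects were already several months past month 12 at the start; for them it exceeds 12 − 6 = 6 months.

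**3. Who is outside.** At least 29 − 27 = 2 of 29 (6.9%). The documents do not say why the cap is 27.

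**4. What one missed subject does.** A fail needs three subjects. Two counted plus one missed reads as a pass, although 3/29 = 10.3% of those implanted had the event.

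**5. Illustration.** The plan gives no sample size calculation, power or event rate beyond month 6, so there is no figure of its own to reproduce. Let r be the 24-month risk per subject of a related SAE with one common root cause, and m the share of event subjects who are missed. Both are assumptions. With X binomial(29, r(1 − m)),

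P(fail) = P(X ≥ 3) = 1 − Σ(k = 0 to 2) C(29, k) pᵏ (1 − p)²⁹⁻ᵏ, where p = r(1 − m).

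For r = 10%, m = 0: 1 − (0.0471 + 0.1518 + 0.2361) = 0.565. For m = 10%, p = 0.09; for m = 25%, p = 0.075.

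| Assumed r | all counted | 10% missed | 25% missed |
|---|---|---|---|
| 5% | 17.5% | 14.0% | 9.4% |
| 10% | 56.5% | 49.1% | 37.2% |
| 15% | 83.2% | 77.0% | 64.8% |

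**6. Why the margin may already be thin.** Section 4.2.2.1.2 reports two SAEs related to the procedure, or to device and procedure, both post-operative wound infections. Assume that they occurred in two subjects, share a root cause and are carried into criterion 1. Then one further case fails it. P(at least 1 of the 27 others) is 1 − 0.98²⁷ = 0.42 at an assumed 2% risk and 1 − 0.95²⁷ = 0.75 at 5%. The plan does not state that CBAS5751 events are carried over, although the wording of the criterion implies it.

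**The case against.** The strongest reply is that the plan does not exclude non-users. Neither 7.2.1 nor 9.5 requires device use, and neither 9.5 nor criterion 1 relies on the enrolled status. The definition in 7.2.5 fits poorly here, since every subject was implanted and fitted in CBAS5751. Section 8.3 is a risk statement, not an eligibility rule. The unaided audiogram, HUI, CSRI and AE review can all be done without the device. Explantation and revision surgery are named safety endpoints. This stands: a reader might infer that only current users can be enrolled and counted, but the documents show an inconsistency, not a clear exclusion. Section 17 does mention a "serious or intolerable ADE, leading to the explant or discontinued use of the device", but as a reason to discontinue the whole investigation; it does not describe a subject who goes uncounted.

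A reader might also infer that everything before Visit 1 is unseen. It is not. Events up to month 6 are in the CBAS5751 record, and footnote d of the schedule, section 9.10 and section 11.2 collect the later months retrospectively for those who join. Section 7.4 starts AE reporting at the first subject's first visit, but these three places outweigh that sentence, so it needs alignment only.

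Nor do the documents suggest that the subjects outside the cap had events. They report no related SAE that ended device use, and both wound infections resolved. A worst case in which every non-participant had the event has no support.

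What the reply leaves open is the subject who never joins. Even if non-users are admitted, one who declines after a serious complication is not counted, and no rule covers that subject.

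**Conclusion.** The point holds as a gap in the definition of criterion 1. Related SAEs in implanted subjects who do not join can be missed, mainly those between the last CBAS5751 visit and Visit 1, and any error favours a pass. The text does not establish that such events have been or will be missed.

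One subject is enough to reverse the result when the true count is three. The fall in P(fail) from 56.5% to 49.1% or 37.2% rests on an assumed 10% risk, an assumed missed share and independence between subjects; it shows sensitivity and is not an estimate. Since this one count can decide the verdict on the whole investigation and the remedy is cheap, the change should be made, even though the study tests no formal hypothesis.

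**What to change.** 1. **Section 9.1, criterion 1.** Replace with: *Fail if more than two of the 29 subjects implanted in CBAS5751 have an SAE related to the device or the procedure, with the same root cause, within 24 months from surgery. SAEs recorded in CBAS5751 count for all 29; SAEs recorded in this investigation count for participants. The report states how many of the 29 have unknown status at month 24.*
2. **Section 7.2.5.** Add: *A subject who no longer uses the device may consent to safety data only and counts as enrolled for section 9.6 and criterion 1.*
3. **Section 7.4.** Start AE reporting at the last CBAS5751 visit, to match section 11.2.

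Optional, and only if the ethics committees agree: a coded count of explantations in non-participants. Section 11.3 already sends explanted implants to device analysis, so return records should show most of them.

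The cost is a few sentences in the CIP and a safety-only consent form, with no new tests. Some subjects' status may stay unknown, especially where use ended without explantation; the unknown-status line is there to show how many.

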7.3.2 Post-Enrolment Evaluations and Procedures

7.3.2.1 Audiometry testing

If the study team experience an "unreasonable value" in any test, the test should be performed again after a short while to confirm validity.

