7.3.2.1.1 Audiogram

To follow how the subject's hearing thresholds change over time, unaided audiometric threshold measures (including both air- and bone conduction thresholds) will be recorded at 12 and 24 months and compared with the same data collected at baseline before implantation in the CBAS5751 investigation.

Frequencies required for air conduction thresholds are 250, 500, 750, 1000, 1500, 2000, 3000, 4000, 6000 and 8000Hz. For bone conduction thresholds the required frequencies are 250, 500, 750, 1000, 1500, 2000, 3000, 4000 and 6000Hz.

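### Only a failed PTA-4 or SNR result triggers a root cause review, and the plan does not say whether the measured or the reviewed result decides the verdict

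*Combined protocol and SAP*

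**What the plan says.** Section 9.1 sets three pass/fail criteria:

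- Safety: fail if "more than two of the subjects have experienced a related serious adverse event with the same root cause".
- PTA-4: fail if "more than two of the subjects have an increase in PTA-4 Sound field threshold >15 dB at 24 months".
- SNR: fail if "more than two of the subjects have an increase in SNR field threshold >1 unit at 24 months".

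PTA-4 and SNR are compared with the last aided value from CBAS5751 (3 or 6 months). For these two, the section adds: "If a failed result regarding PTA-4 or SNR is obtained a root cause analysis will be performed". The analysis is meant to confirm that the value reflects declined performance and "not on other factors such as impaired unaided hearing, incorrectly performed tests or other causes". The section then states: "If any of the criteria are failed the investigation is considered as fail". It also says that no SAP will be written.

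Section 7.3.2.1 has a separate retest rule. If the team meets an unreasonable value in any test, "the test should be performed again after a short while to confirm validity". Unreasonable is not defined, and the value to be kept is not stated.

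Several relevant records cover all subjects, whether they pass or fail. Under 7.3.2.1.1, "unaided audiometric threshold measures (including both air- and bone conduction thresholds) will be recorded at 12 and 24 months", for comparison with the pre-implant audiogram. The Schedule of Events lists blocking verification at both visits. Section 13 requires incorrectly completed assessments to be documented as deviations.

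**The concern.** The review depends on the result. A subject who exceeds a limit may have the value explained by poorer unaided hearing, a test error or something unlisted. A subject within the limit gets no comparable review, although the same kinds of fault could hide a decline. A step applied only to failures can remove failing subjects from the count but cannot add any.

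The plan names no reviewer and no standard of evidence, and does not say what a finding does to the verdict. The study is open, and Section 7.1 rules out a data monitoring committee. With no SAP planned, no later document is foreseen to settle the matter. The choice between measured and reviewed results could therefore be made after the 24-month values are known. These criteria are the plan's only stated success rule.

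**Working it through.** The documents give no error rate, power or test-retest SD for these criteria, so there is no planned figure to reproduce. The calculations below are illustrations.

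**Inputs.** From the documents: at most 27 subjects (7.1, 7.2.3); fail at three or more subjects; limits of 1 unit for SNR and 15 dB for PTA-4 (9.1). Assumed: one SNR unit is 1 dB; changes are normal and independent between subjects; all 27 attend at 24 months; SDs as shown.

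**1. SNR with no true change.** For paired-difference SD s, the chance that one subject exceeds the limit is p = 1 − Φ(1/s). The chance of a fail is P(X ≥ 3) with X ~ Binomial(27, p).

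| s (dB) | p | Expected subjects, 27p | P(fail) |
|---|---|---|---|
| 0.5 | 0.023 | 0.6 | 2% |
| 1.0 | 0.159 | 4.3 | 82% |
| 1.5 | 0.252 | 6.8 | 98% |
| 2.0 | 0.309 | 8.3 | 99.6% |

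For s = 1.0, the probabilities of 0, 1 and 2 exceedances are 0.009, 0.048 and 0.118, so P(fail) = 1 − 0.175 = 0.825. Unless the test is very repeatable, the review is likely to be triggered without any decline.

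**2. PTA-4 with no true change.** For within-subject SD w, the paired-difference SD is √2·w and p = 1 − Φ(15/(√2·w)). At w = 3 dB, p = 0.0002 and P(fail) is practically zero. At w = 5 dB, p = 0.017 and P(fail) = 1.1%. At w = 7 dB, p = 0.065 and P(fail) = 25%.

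**3. What a review of failures could do if it changed the count.** Let each subject exceed a limit with probability p, and let the review set aside a share q of exceedances. Then P(fail) = P(X ≥ 3) with X ~ Binomial(27, p(1 − q)).

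| p | q = 0 | q = 1/3 | q = 1/2 |
|---|---|---|---|
| 0.10 | 52% | 27% | 15% |
| 0.15 | 79% | 52% | 33% |

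Both p and q are assumed. The direction does not depend on them: for any q above zero, P(fail) falls.

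**4. Retest.** A simulation of 200,000 trials took SNR with no true change and within-subject SD 1.0 dB, and replaced each retested value by its repeat. P(fail) was 97.3% with no retest, 60.6% when only worsenings above 1 dB were repeated, and 69.6% when all changes above 1 dB in either direction were repeated. Moves from pass to fail were zero under the one-sided rule and 0.3% of trials under the two-sided rule. Both triggers, and keeping the second value, are assumptions. The result depends on choices the plan leaves open.

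**The case against.** Four objections have force.

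First, a reader might infer that the plan lets the review overturn a fail. It does not say so. Read literally, the sentence that any failed criterion fails the investigation keeps the measured fail. Reversal is only an inference from the aim of confirming declined performance. What is shown is an undefined consequence, not a demonstrated bias.

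Second, a reader might infer that passing values go unchecked. The documents do not support that: blocking verification, unaided audiograms and deviations are recorded for everyone, and individual data are listed. Only the added review is confined to failures.

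Third, a reader might take the retest rule as working only towards a pass. As written it covers any test and has no direction, so an implausibly good value could also be repeated. Selective use in an open study is a risk, not a stated rule.

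Fourth, the SNR figures cut the other way too. If noise alone fails a stable device most of the time, the measured rule leans towards fail, and a review is a reasonable corrective. This stands. It argues against simply binding the verdict to measured values, but a corrective applied to every subject under limits fixed in advance is safer than a discretionary one confined to failures.

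Also, the safety criterion has no such review sentence, and the study plans no formal hypothesis testing.

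**Conclusion.** The concern holds in limited form. For PTA-4 and SNR, review is triggered only by failure, its list of causes is open, and its effect on the verdict is unstated. If it has an effect, that effect can only favour a pass on these two of the three criteria. The documents do not show that a fail will be reversed or that the verdict is biased.

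The practical exposure is mainly SNR, with a noise-only P(fail) of 82% to 99.6% at an assumed paired-difference SD of 1.0 to 2.0 dB. It would be small if the SD were near 0.5 dB (2%). For PTA-4 it is at most 1.1% at an assumed within-subject SD of 3 to 5 dB. The set-aside shares in the third calculation only illustrate how far a verdict could move. The plan should be changed because the remedy is cheap and the deciding step is otherwise left open until results are known.

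**What to change.** **Section 9.1, verdict.** Report the PTA-4 criterion, the SNR criterion and the overall verdict twice: on measured values and after review. State, before any 24-month data are seen, which is the formal verdict.

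**Section 9.1, review.** Apply the same prespecified check to every subject, passing or failing, with limits fixed in advance and using data already collected:

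- the change in unaided bone conduction PTA-4 of the cochlea that the device stimulates, which is the contralateral one in SSD (Section 5.1);
- the blocking verification;
- the recorded test deviations.

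State that the bone conduction baseline is pre-operative while the aided baseline is at 3 or 6 months, so the two changes cover different periods, with surgery between their baselines. BC Direct is not a substitute, because its tones pass through the sound processor (7.3.2.1.3.2).

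**Section 7.3.2.1, retest.** Replace the undefined term with a numeric trigger that works in both directions. Record both runs and state in advance which value is analysed, without averaging in a run documented as invalid.

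**Cost.** Protocol wording, one derived variable and one extra table, with no routine test added to the schedule. The sponsor gives up the discretion to set aside failed results only.
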